#### **12.4. Statistical Analysis Plan**

All statistical analysis will be conducted by the ICR-CTSU at The Institute of Cancer Research (or in collaboration with the statistical team at ICR-CTSU). Analysis methods are outlined here, in brief. Full details will be specified in a Statistical Analysis Plan in accordance with ICR-CTSU Standard Operating Procedures.

The timing of the principal efficacy analysis is planned to be event-driven, with the required number of events expected to be achieved when all participants have a minimum of approximately 3.5 years follow-up in the trial. The Independent Data Monitoring Committee (IDMC) will monitor the accumulation of follow-up data and primary endpoint events in the trial and will advise on when the dataset is sufficiently mature for analysis.

Efficacy analyses, including the primary endpoint comparison, will include all randomised participants according to allocated treatment arm (intention-to-treat). Toxicity analyses will be performed on a per protocol analysis set, to be defined within the Statistical Analysis Plan.

The primary endpoint, as well as other time-to-event endpoints, will be presented by treatment arm using Kaplan-Meier curves; estimated 5-year event rates will be given along with 95% confidence intervals. Hazard ratios (presented with 95% confidence intervals and p-values) will be estimated from Cox proportional hazards model with adjustment for minimisation factors. Proportional hazards assumptions will be checked and, if violated, appropriate alternative methods will be applied.

Acute toxicity data will be analysed when all participants have reached the 12-week visit. Late toxicity data will be analysed when all participants have reached the 2-year visit (or been lost to follow-up/withdrawn prior to this time). Acute and late toxicity data will be summarised as grade and grade  $\geq 2$  frequencies and percentages at each time point. Worst grade adverse events occurring within each period (acute and late) will also be summarised. For each period, the proportion experiencing GI and GU toxicity (grade  $\geq 2$ ) will be presented along with the difference in proportions with 90% confidence intervals (reflecting a one-sided 5% significance level). The relative difference between treatment groups will be estimated using logistic regression models; odds ratios with 90% confidence intervals will be presented.

Radiotherapy planning and delivery data will be presented with standard summary statistics; no formal comparisons between arms will be made. Similarly, since numbers of second primary cancers are expected to be small, these will be reported by treatment arm without formal comparison.

Any quality of life data collected from PACE-NODES participants within the SPRUCE study will be shared with PACE-NODES for analysis. Analysis of QoL data is further detailed in section 19.2.

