### **9.5. Radiotherapy Planning**

Radiotherapy planning and outlining should be carried out in accordance with the guidelines in the current version of the radiotherapy planning document, available on request from ICR-CTSU ([[contact]](mailto:[contact])) and via the RTTQA website (<http://www.rtrialsqa.org.uk/rttqa/>).

- Radiotherapy will be planned according to randomisation allocation, using pre-specified planning constraints for the target volumes and organs at risk. In patients where mandatory constraints are not met, cases will be discussed on an individual basis with the trial clinical and RTTQA team.
- If there are planning issues in relation to SBRT for pelvic nodes for patients randomised to the PPN-SBRT arm and the treatment cannot be delivered, alternative treatment options should be discussed with the Chief Investigator and/or Clinical Coordinators and the RTTQA team. Please see the RTQA guidance notes for further information.
- Dose constraints will be based on those from the PACE-C trial, with additional constraints for PPN-SBRT from the SPORT trial. Bowel constraints are stricter than previously reported studies in order to prioritise bowel tolerance.
- Peri-rectal spacers are permitted as part of the treatment for patients where this will not compromise target coverage or toxicity, and must not be used in patients with posterior T3a/T4 disease. In centres using peri-rectal spacers, this must be used for patients randomised to either arm i.e. the decision to use a peri-rectal spacer must be made prior to randomisation.

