### **12.1.3. Power for secondary toxicity analysis**

This number of patients also gives adequate power for secondary toxicity comparisons, aimed at demonstrating “non-inferiority” of PPN-SBRT in terms of late gastrointestinal toxicity (CTCAE grade 2+), as follows:

Assuming a 92% evaluable rate (based on expected recurrence-free rate at 2 years and allowing for some loss to follow-up), 1038 patients would be evaluable for toxicity comparison up to 2 years. Assuming a P-SBRT toxicity rate of 13% (based on data from PACE-B [19]), the trial will have more than 85% power, with a one-sided 5% significance level, to rule out a PPN-SBRT toxicity rate of >19%, i.e. accepting an increase of up to 6% worse.

If toxicity rates are lower we will still have very good power (at least 90%) to rule out a doubling in toxicity. This relative non-inferiority margin (“a doubling”) is informed by POP-RT where the cumulative late RTOG grade 2+ gastrointestinal toxicity was 6.5% for WPRT and 3.8% for PORT [20]. Unless absolute rates are very low, we will have good power (>80%) to rule out smaller relative effects (E.g. with a 10% P-SBRT toxicity rate, we would have >80% power to rule out a 50% increase, to 15%, with PPN-SBRT).

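### The only analysis set named for the late-GI non-inferiority comparison is per protocol, although nodal treatment can prove undeliverable after randomisation in the PPN-SBRT arm alone

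*Protocol*

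**What the plan says.** Section 12.4 analyses efficacy by intention to treat. For toxicity it says: "Toxicity analyses will be performed on a per protocol analysis set, to be defined within the Statistical Analysis Plan". The choice of set is made in the protocol; only its membership is deferred. No other toxicity set and no sensitivity analysis is named.

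Section 12.3.2 makes late GI toxicity of CTCAE grade 2 or above a key secondary endpoint. Section 12.1.3 frames the comparison as non-inferiority of PPN-SBRT. Starting from an assumed P-SBRT rate of 13%, it claims power above 85% at a one-sided 5% level; the target is "to rule out a PPN-SBRT toxicity rate of >19%, i.e. accepting an increase of up to 6% worse". The evaluable number behind this is introduced as follows: "Assuming a 92% evaluable rate (based on expected recurrence-free rate at 2 years and allowing for some loss to follow-up". Per protocol exclusions are not part of that allowance.

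Section 9.5 has radiotherapy planned according to the allocated arm. It then provides that, where nodal planning problems arise "for patients randomised to the PPN-SBRT arm and the treatment cannot be delivered, alternative treatment options should be discussed" with the trial's clinical leads and the radiotherapy quality assurance team. It adds that the bowel constraints are stricter than in earlier reported studies.

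Three other places bear on the point. Exclusion criterion 5 (section 5.4) removes, before randomisation, men whose diagnostic MRI shows bowel so close to the target that pelvic treatment is very unlikely to be deliverable. Section 12.3.2 lists deviations from the allocated arm among the feasibility data. Section 8.4 keeps men who discontinue treatment in follow-up.

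**The concern.** Whether a nodal plan can be delivered is learned after randomisation, and only for men allocated to PPN-SBRT. A P-SBRT man with the same anatomy never has a nodal plan made, so he cannot be recognised or removed. If the SAP defines the per protocol set by receipt of allocated treatment, a usual definition, the exclusions fall on one arm and the arms compared are no longer those formed by randomisation.

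The likely reasons for non-delivery make this more than a formality. Section 9.5 stresses bowel constraints, and section 12.3.2 ties the concern about GI toxicity to bowel dose. If the excluded men would have had more GI toxicity than average even with prostate-only treatment, removing them lowers the PPN-SBRT rate for a reason unrelated to treatment. The claim at stake is the trial's main safety statement: that nodal treatment does not raise late GI toxicity by more than the accepted amount.

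**Working it through.** **Inputs from the protocol.** 1128 randomised 1:1 (sections 5.1 and 12.1.1); 92% evaluable, 13% P-SBRT rate, 6-point margin, one-sided 5% (section 12.1.3).

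**The plan's own figure.** 1128 × 0.92 = 1037.8, so 1038 evaluable, or 519 per arm. With 13% in both arms:

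- SE = √(2 × 0.13 × 0.87 / 519) = 0.0209
- Power = Φ(0.06/0.0209 − 1.645) = Φ(1.229) = 89%
- With the variance under the null taken at 13% versus 19%, power = 86%

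Both agree with the stated figure of more than 85%. The power statement is not in dispute.

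**Assumptions the protocol does not supply.** Let f be the share of PPN-SBRT men who leave the per protocol set because nodal treatment was undeliverable. Let RR be their GI risk under prostate-only treatment relative to other men. All P-SBRT men stay in.

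**Shift in the difference.** The rate under prostate-only treatment in deliverable men is c = 0.13 / [(1 − f) + f × RR]. With no treatment effect at all, the per protocol difference is c − 0.13 instead of zero.

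Example, f = 5% and RR = 2: c = 0.13/1.05 = 12.38%, a shift of −0.62 points.

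**One-sided error.** Suppose the true effect in deliverable men is exactly 6 points, so that non-inferiority should be declared 5% of the time. The PPN-SBRT rate is p = c + 0.06 in 519 × (1 − f) men. The probability of declaring non-inferiority is Φ[(0.06 − (p − 0.13))/SE − 1.645], with SE = √(0.13 × 0.87/519 + p(1 − p)/(519(1 − f))).

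Same example: p = 18.38%, SE = 0.02285, Φ(0.271 − 1.645) = 8.5%.

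| f | RR 0.5 | RR 1 | RR 1.5 | RR 2 |
|---|---|---|---|---|
| 2% | +0.13 pts; 4.4% | 0; 5.0% | −0.13; 5.6% | −0.25; 6.3% |
| 5% | +0.33; 3.7% | 0; 5.0% | −0.32; 6.6% | −0.62; 8.5% |
| 10% | +0.68; 2.7% | 0; 5.0% | −0.62; 8.4% | −1.18; 12.9% |

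Each cell gives the shift in percentage points, then the one-sided error.

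**Analysis by allocation.** If undeliverable men receive treatment with prostate-only toxicity, the 6-point effect is diluted to 6 × (1 − f): 5.88, 5.70 and 5.40 points at f = 2, 5 and 10%. With 519 per arm, the probability of declaring non-inferiority is 5.6, 6.5 and 8.4%. This set also leans toward non-inferiority, by a different route.

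**Requiring both.** The probability that both analyses meet the margin cannot exceed the smaller of the two. At f = 10% and RR = 2 that is at most 8.4% rather than 12.9%; at RR = 1 it is at most 5.0% for any f shown.

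**Power.** Dropping 2, 5 or 10% of the PPN-SBRT arm leaves 88.8, 88.3 and 87.5% on the first formula, so the issue is bias and not precision.

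**The case against.** The strongest reply is that the protocol does not say these men leave the set. A reader might infer from sections 9.5 and 12.4 together that PPN-SBRT men with undeliverable nodal plans are dropped while their P-SBRT counterparts stay. The text does not go that far: membership is left to the SAP, which is not at hand, and section 9.5 says only that alternatives are discussed. That stands, and the point is therefore about what the set can do, not what it does. It is still a protocol matter, because the protocol itself names per protocol as the set and names no other.

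Second, the direction is not given. Bias toward non-inferiority needs excluded men to have above-average GI risk without nodal treatment. Bowel near the nodal volume may matter mainly when the nodes are irradiated, and exclusion criterion 5 already removes the clearest cases from both arms. This also stands: with equal risk there is no bias, and with lower risk it reverses.

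Third, a per protocol set is a usual choice for non-inferiority because it avoids dilution. That is correct, and it is why replacing it by an allocation-based set would not be enough.

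Two further readings are tempting and not supported. One is a much larger bias: 5–10% excluded with GI rates of 26–39% would give 0.7–2.9 points. Those rates imply 2.1 to 3.9 times the risk of the remaining men, for which the documents offer no basis. The other is that the 92% evaluable rate shows men with recurrence will be excluded. Section 12.1.3 uses it as a power assumption; section 12.4 mentions only loss to follow-up and withdrawal before the 2-year visit, and states no exclusion for recurrence.

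**Conclusion.** The point holds as a conditional weakness that is worth correcting. The protocol fixes one analysis set for its toxicity non-inferiority comparison, and that set is open to exclusions after randomisation that can arise in one arm only. With 2–10% of PPN-SBRT men excluded and a relative risk of 1.5–2, the shift is about 0.1–1.2 points of the 6-point margin, and the one-sided error is about 5.6–12.9% against a nominal 5%. Both ranges are assumptions, since the protocol gives no rate of non-delivery and no risk for these men. The documents do not support saying that randomisation is broken or that the comparison is certainly biased. The stated power is correct and barely affected.

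**What to change.** In section 12.4, add a toxicity analysis of all randomised participants who started any radiotherapy, whether trial or alternative, by allocated arm. Restricting it to men who received at least one SBRT fraction would not do: if the alternative is not SBRT, the same men would drop out of the same arm. Count late GI events up to 24 months whether or not recurrence has occurred, and say so, which also settles how the 92% in section 12.1.3 should be read.

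Keep the per protocol analysis, and require that its membership should not, as far as possible, depend on deliverability that can be assessed in one arm only. Claim late-GI non-inferiority only if both analyses meet the margin, since one is exposed to selection and the other to dilution. Report the number of undeliverable nodal plans beside the result; deviations from the allocated arm are already collected.

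The cost is one further analysis on data already collected and a change of wording in the protocol and SAP. The downside is that the claim must hold in two sets, so it is somewhat harder to make.

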## **12.3. Endpoint Definitions**

### **12.3.1. Primary endpoint**

Time to biochemical or clinical failure: defined as time from randomisation to first of biochemical failure, recommencement of androgen deprivation therapy, local recurrence, lymph node/pelvic recurrence, distant metastases or death due to prostate cancer. Recurrence identified on PSMA PET or wbMRI are included as events. For participants who are not known to have had an event at the time of analysis (including those lost to follow-up), observations will be censored on the date of most recent follow-up visit.

Biochemical failure is the most sensitive indicator of recurrent prostate cancer, encompassing clinical and radiological relapse, and is aligned with the primary outcome in PACE-C and PIVOTALboost.

Biochemical (PSA) failure will be defined following the RTOG-ASTRO Phoenix Consensus definition: an increase in serum PSA  $\geq 2$  ng/ml greater than the post-treatment nadir. PSA failure will be confirmed with a second measurement ( $>4$  weeks from the index measurement) also meeting the criteria for PSA failure.

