### **12.3.2. Secondary endpoints**

A key secondary endpoint is late gastrointestinal (GI) toxicity, grade  $\geq 2$  (CTCAE, clinician assessed).

Assessment of GI toxicity is particularly important with PPN-SBRT given the increased bowel dose compared to prostate alone radiotherapy. CTCAE is a recognised standard used in other relevant trials. Given the potential for discrepancies between clinician and patient reported toxicity [21], patient reported outcomes measures (PROMs) as a measure of the direct impact on patient quality of life [22] will provide complementary information to clinician assessed toxicity.

Other secondary endpoints include:

- Time from randomisation to first of: recommencement of androgen deprivation therapy; biochemical failure; loco-regional recurrence (recurrence in the prostate and/or pelvic lymph nodes).
- Metastatic relapse-free survival, defined as time from randomisation to distant metastases or death from prostate cancer.
- Prostate cancer-specific survival, defined as time from randomisation to death due to prostate cancer.
- Overall survival, defined as time from randomisation to death from any cause.
- Acute toxicity, occurring within the first 12 weeks of follow-up (CTCAE and RTOG), with a focus on GI and GU toxicity, grade  $\geq 2$ .
- Late toxicity, reported from the 6 month visit onwards (CTCAE and RTOG), with a focus on GI and GU toxicity, grade  $\geq 2$ .
- Quality of life measured using the following questionnaires: the International Prostate Symptom Score (IPSS), the 5-item version of the International Index of Erectile Function (IIEF-5), the short form Expanded Prostate Index Composite-26 (EPIC-26) and the EQ-5D-5L (see section 19.2 for further details).

- Radiotherapy planning and delivery data (PTV for prostate and pelvic nodes; adherence to dose constraints; and deviations from allocated treatment arm) to demonstrate feasibility.
- Second primary cancers occurring during trial follow-up.

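### Kaplan-Meier 5-year rates for endpoints that do not count other-cause death modestly overstate the actual probability of failure; cumulative incidence should be reported as well

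*Protocol*

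**What the plan says.** Section 12.4 names one display for every time-to-event endpoint: "The primary endpoint, as well as other time-to-event endpoints, will be presented by treatment arm using Kaplan-Meier curves; estimated 5-year event rates" follow, with 95% confidence intervals. Hazard ratios "will be estimated from Cox proportional hazards model with adjustment for minimisation factors".

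Section 12.3 defines the endpoints. The primary endpoint is the first of biochemical failure, restarting ADT, "local recurrence, lymph node/pelvic recurrence, distant metastases or death due to prostate cancer"; death from another cause is not an event. For anyone without a known event, "observations will be censored on the date of most recent follow-up visit". Other-cause deaths are not named in that rule, but they fall under it. The rule is written for the primary endpoint only.

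Among the secondary endpoints in section 12.3.2, metastatic relapse-free survival is "defined as time from randomisation to distant metastases or death from prostate cancer" and prostate cancer-specific survival is "defined as time from randomisation to death due to prostate cancer". The combined ADT, biochemical failure and loco-regional recurrence endpoint includes no death. Overall survival counts any death. Section 12.3.2 gives no censoring rule, and the protocol does not mention competing risks or cumulative incidence.

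**The concern.** A man who has died of another cause can no longer relapse. If he is censored, Kaplan-Meier lets the men still at risk stand in for him, as though he could still fail. One minus Kaplan-Meier then estimates the risk in a setting without other-cause death, and does so only if the causes are independent. Read as the proportion of men who will fail within 5 years, it is too high whenever other-cause deaths occur.

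Such deaths are foreseeable. Section 5.4 excludes men with a life expectancy below 5 years, but section 5.3 admits WHO performance status up to 2, and Appendix A3 lists MI and CVA among the expected events with ADT.

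What is at stake is the absolute benefit. Section 12.1.1 justifies the target effect as large enough to offset a probable rise in toxicity, and section 12.4 reports toxicity as observed proportions. Benefit would be shown on a net-risk scale and harm on an observed scale.

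**Working it through.** **Inputs from the protocol (section 12.1.1).** Control 5-year event-free rate 85%; target HR 0.6; two-sided 5%; 80% power; 1:1 allocation; 564 per arm; 37 months of staggered recruitment plus 41 months minimum follow-up (78 months in all); 3% loss to follow-up at 5 years.

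**Assumption.** Other-cause mortality is not given. I take 3% to 12% at 5 years, with constant hazards and the same rate in both arms. The life-expectancy exclusion argues against the high end.

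**The plan's own figures first.**
- Freedman's formula: (1.96 + 0.8416)² × [(1 + 0.6)/(1 − 0.6)]² = 7.849 × 16 = 125.6, which rounds up to the stated 126 events.
- Exponential failure with the stated accrual, follow-up and loss gives 78.3 control events and 126.8 in total, against the stated 78 and 126.
- PPN-SBRT event-free rate: 0.85^0.6 = 0.907, against the stated 91%. The failure rates are therefore 15.00% and 9.29%, a difference of 5.71 points.

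**Kaplan-Meier against cumulative incidence.** Let λ be the failure hazard and μ the other-cause death hazard, per year.
- λ = −ln(0.85)/5 = 0.03250 (P-SBRT); 0.6λ = 0.01950 (PPN-SBRT); μ = −ln(1 − d)/5 for other-cause mortality d.
- One minus Kaplan-Meier at 5 years: 1 − exp(−5λ).
- Cumulative incidence at 5 years: λ/(λ + μ) × [1 − exp(−5(λ + μ))].

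Example, d = 12%, P-SBRT: μ = 0.02557; 0.03250/0.05807 × (1 − 0.85 × 0.88) = 0.5597 × 0.252 = 14.11%.

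| Assumed d | P-SBRT | PPN-SBRT | Difference | Overstatement in points (P-SBRT / PPN-SBRT / difference) |
|---|---|---|---|---|
| 0% (equals Kaplan-Meier) | 15.00% | 9.29% | 5.71 | none |
| 3% | 14.78% | 9.15% | 5.63 | 0.22 / 0.14 / 0.08 |
| 5% | 14.63% | 9.06% | 5.57 | 0.37 / 0.23 / 0.14 |
| 8% | 14.41% | 8.92% | 5.49 | 0.59 / 0.37 / 0.22 |
| 10% | 14.26% | 8.83% | 5.43 | 0.74 / 0.47 / 0.28 |
| 12% | 14.11% | 8.73% | 5.37 | 0.89 / 0.56 / 0.33 |

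A simulation with 200,000 men per arm under the trial's accrual and censoring agrees. At d = 10% it gives one minus Kaplan-Meier of 15.0% against Aalen-Johansen 14.2% in P-SBRT, and 9.3% against 8.9% in PPN-SBRT.

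**Scale.** The binomial standard error with 564 men is √(0.15 × 0.85/564) = 1.5 points for P-SBRT and √(0.093 × 0.907/564) = 1.2 points for PPN-SBRT. For the difference it is √(1.5² + 1.2²) = 1.9 points. Censoring before 5 years would widen these. The largest shifts, 0.89, 0.56 and 0.33 points, are about 0.6, 0.5 and 0.2 of the matching standard error.

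**The case against.** - **It belongs in the SAP.** Section 12.4 calls itself a brief outline and leaves full details to a SAP that is not shown. That SAP may add cumulative incidence, and nothing in section 12.4 forbids it. This stands in part. But the protocol names the estimator and applies it to every time-to-event endpoint, so a SAP that simply follows it inherits the problem.
- **Censoring of other-cause deaths is inferred.** This stands. The text supports the inference for the primary endpoint. For the secondary endpoints no rule is given, and censoring is only the natural reading of the definitions.
- **Kaplan-Meier is not wrong in itself.** It is a valid net-risk estimate if the causes are independent, and it is the natural counterpart of the 85% and 91% event-free design rates. This stands, and is why the curve should be kept. The fault lies in presenting its complement as the actual probability of failure.
- **The size is negligible.** At 5 years the shift is indeed below one standard error.

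Two stronger readings are tempting. A reader might infer that the primary comparison is biased. It is not: with other-cause deaths censored, the Cox model estimates the cause-specific hazard ratio, which is a legitimate target, and the events needed at HR 0.6 stay at 126. A reader might also point to long-term capture through routine data and argue that the gap will become large. The protocol plans 5-year rates and trial-specific follow-up to 5 years; it specifies no later failure estimate, so no later figure can be held against it.

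**Conclusion.** The point holds as a modest reporting matter. Where other-cause deaths are censored, the Kaplan-Meier 5-year rates in section 12.4 overstate the actual probability of failure in both arms and, slightly, the absolute benefit. For an assumed 3% to 12% other-cause mortality, the excess is about 0.2 to 0.9 points in P-SBRT, 0.1 to 0.6 points in PPN-SBRT and 0.1 to 0.3 points in the 5.7-point difference.

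The direction follows from the endpoint definitions together with the implied censoring. The size depends on the assumed mortality, on constant hazards and on equal other-cause mortality in the two arms. Overall survival is not affected. Nothing here threatens the primary test or the sample size.

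**What to change.** - In section 12.4, report 5-year cumulative incidence (Aalen-Johansen) by arm with 95% confidence intervals for the primary endpoint, metastatic relapse or prostate cancer death, prostate cancer death, and the ADT, biochemical and loco-regional endpoint. Treat other-cause death as the competing event; for the endpoint that counts no death, any death competes.
- In section 12.3, state for each of these endpoints how other-cause deaths are handled.
- Keep the cause-specific Cox model for the hazard ratio, Kaplan-Meier for overall survival, and the Kaplan-Meier event-free curve alongside for comparison with the 85% and 91% design rates.

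The cost is a few sentences in the protocol and SAP and a few lines of code. Date and cause of death are already needed for overall and prostate cancer-specific survival, so no new data, patients or events are required. The change is best made before the event-driven analysis.

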### 5.2. Source of Participants

Participants will be recruited from approximately 40 participating sites in the UK, and additional international centre participation from Ireland and New Zealand.. Potential participants will be identified in oncology clinics and discussed at Multi-Disciplinary Team (MDT) meetings.

ICR-CTSU encourages investigators to consider equality, diversity and inclusion when recruiting participants into its trials.

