#### 12.1.1. *Sample size for primary efficacy analysis*

The sample size calculation is based on assessing time to biochemical or clinical failure (primary endpoint), as defined below. In POP-RT, 5-year biochemical failure-free survival in the control arm was 81% [10]. Allowing for some improvement in outcomes over time, as suggested by recent data from PACE-B which showed very good outcomes in the lower-risk group [18] the 5-year event-free rate in the P-SBRT control arm is assumed to be 85%. The target hazard ratio (HR) for the trial is 0.6, corresponding to a 6% improvement (to 91%) in the 5-year event rate with PPN-SBRT. Although a larger effect (HR=0.23) was seen in POP-RT, the PACE-NODES design will ensure that a smaller but clinically meaningful effect is not missed. The target effect size is similar to that for PIVOTALboost (HR=0.625), which is testing the same question in the 20f setting in a lower risk group of patients, reflecting the magnitude of effect considered appropriate to counterbalance a likely increase in toxicity.

The sample size was calculated using the `artsurv` package (v1.1.0) within Stata software and was based on the following design parameters and assumptions:

- 1:1 allocation ratio
- staggered recruitment over 37 months in proportions of 5%, 13%, 16%, 21%, 21%, 21%, 3% per 6-month period (noting that recruitment is expected to be complete within the first month of the final period)
- 41 months minimum follow-up
- 80% power
- 5% 2-sided significance
- Expected 3% loss to follow-up at 5 years (based on CHHiP)

In order to achieve 80% power, 78 control arm events are required for the analysis (126 events expected in total), and we anticipate that this will be achieved through recruitment of 1128 patients, followed up for a minimum of approximately 3.5 years.

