## **12.2. Treatment Allocation**

All trial participants will receive Stereotactic Body Radiotherapy (SBRT).

Participants will be randomised between 5 fraction prostate SBRT (P-SBRT) or 5 fraction prostate and pelvic nodal SBRT (PPN-SBRT) on a 1:1 basis using minimisation with a random element. Balancing factors in the minimisation algorithm will be: centre, radiological staging method (PET-CT and/or whole body MRI; other), use of peri-rectal spacers (yes; no), use of chemotherapy/ARTA (yes; no), and planned duration of ADT (<2 years; ≥2 years).

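### The primary Cox model leaves out Gleason grade, T stage and PSA and does not say how centre enters: a small, nearly cost-free improvement

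*Protocol*

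**What the plan says.** Section 12.4 gives one model for the primary endpoint and the other time-to-event endpoints. Hazard ratios, with confidence intervals and p-values, "will be estimated from Cox proportional hazards model with adjustment for minimisation factors". No other test of the primary endpoint is named. The same section says that methods are only outlined and that full detail will follow in the SAP.

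Section 12.2 lists the factors: "Balancing factors in the minimisation algorithm will be: centre, radiological staging method", then peri-rectal spacer, "use of chemotherapy/ARTA (yes; no), and planned duration of ADT". All except centre have two levels.

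Section 5.2 expects "approximately 40 participating sites in the UK, and additional international centre participation from Ireland and New Zealand". It gives no number of international centres.

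Section 12.1.1 sets the information available: "The target hazard ratio (HR) for the trial is 0.6", and "78 control arm events are required for the analysis (126 events expected in total").

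Section 5.3 defines high risk by Gleason 8-10, stage T3a/b or T4, or PSA above 20 ng/ml, alone or in combination. Section 8.1 requires pathology with Gleason scoring, a staging MRI and a pre-ADT PSA before randomisation.

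**The concern.** Eligibility is met by any one of three tumour features, or by all three, so prognosis will vary within the trial. The features that describe this variation are neither balanced by the minimisation nor in the stated covariate set. A Cox model that omits strong prognostic factors gives a hazard ratio slightly closer to 1, loses some power, and leaves any chance imbalance in the estimate.

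Centre raises a separate question. It has by far the most levels of the five factors, and the sentence does not say whether it enters as indicator terms, strata or a random effect. With few events per centre the choice affects the standard error, and a centre with no event has no finite indicator coefficient. The sentence produces the primary p-value, so both matters are best settled before anyone sees outcome data by arm.

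**Working it through.** **1. The plan's own event target.** Freedman's formula with HR 0.6, two-sided 5% and 80% power: (1.960 + 0.842)² × [(1 + 0.6)/(1 − 0.6)]² = 7.85 × 16 = 125.6, so 126 events. With exponential hazards, 85% event-free at 5 years, the stated accrual, 41 months' minimum follow-up and 3% loss, expected events are 78.3 (control) and 48.4 (PPN-SBRT), about 127. Both figures in 12.1.1 reproduce.

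**2. Events per parameter if centre were indicator terms.** Parameters = 1 (treatment) + 4 (binary factors) + (K − 1) centre terms. K is an assumption, because 5.2 gives only the approximate UK number.

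| K | Parameters | Events per parameter |
|---|---|---|
| 40 | 44 | 126/44 = 2.9 |
| 45 | 49 | 126/49 = 2.6 |
| 50 | 54 | 126/54 = 2.3 |

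**3. Simulation of the model choices.** 1128 patients, about 126 events, minimisation with a random element, unequal centres. Assumed, not from the protocol: centre sizes; centre log-hazard SD 0 or 0.3; one binary tumour-risk factor with 50% prevalence and HR 2 or 3. Three 45-centre scenarios of 4,000 runs each are pooled (12,000 runs per column).

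| Model | Rejected at HR 1 | Rejected at HR 0.6 |
|---|---|---|
| Four binary factors | 4.67% | 78.97% |
| + fixed centre terms | 5.33% | 79.75% |
| Stratified by centre | 4.92% | 78.30% |
| Four factors + risk factor | 4.80% | 79.58% |
| Fixed centre terms + risk factor | 5.57% | 80.30% |

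Paired differences from the four-factor model:
- Fixed centre terms: type I error +0.67 points (SE 0.10).
- Stratification: power −0.67 points (SE 0.18).
- Risk factor: power +0.62 points (SE 0.17).

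The higher rejection rate at HR 0.6 with fixed centre terms comes from a test running above its nominal level, so it should not be read as a gain. By scenario, type I error with fixed centre terms was 4.9 to 5.6%. The model standard error was 2 to 5% below the empirical SD, and 95% interval coverage was 93.7 to 95.1%. The estimate moved slightly away from 1 (for example 0.599 to 0.592). Only 31 to 36 of 40 to 45 centres had any event.

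A second set of simulations used 45 centres, centre SD 0.3 and separate Gleason, T stage and PSA effects. It gave type I error of 5.6% with fixed centre terms against 5.1% stratified, and stratifying cost about half a point of power.

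**4. Power from tumour-risk covariates, by assumed strength.**

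| Assumed prognostic HRs | Without | With | Gain (points) |
|---|---|---|---|
| One factor, 2 or 3 (pooled) | 79.0% | 79.6% | 0.6 |
| Three factors: 2.0, 1.8, 1.5 | 80.0% | 80.9% | 0.9 |
| One factor, 5 (40 centres, SD 0.5) | 74.8% | 77.1% | 2.3 |
| Three factors: 3.0, 2.5, 2.0 | 77.9% | 81.3% | 3.4 |

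**5. The two changes together** (stratified by centre, with the risk factor). Type I error over the three 45-centre scenarios: (5.48 + 4.75 + 5.03)/3 = 5.1%. Power against the four-factor model is 78.2% against 77.9% at risk HR 3, and 77.0% against 74.8% at risk HR 5. With moderate effects the two changes nearly offset each other.

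**6. Chance imbalance.** For a factor with 50% prevalence that the minimisation does not balance, the SD of the difference between arms is √(2 × 0.25/564) = 3.0 points, so 95% of trials fall within ±5.8 points. At that limit (52.9% against 47.1%) and prognostic HR 2, the mean hazards stand as 1.529/1.471 = 1.04. A true 0.60 would then appear as about 0.62 or 0.58 without adjustment.

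**The case against.** The strongest reply is that nothing here is an error. Adjusting for the factors used in allocation is a sound, pre-specified choice. Omitting other prognostic factors leaves a randomised comparison valid (4.67% type I error above), and the attenuation it causes is conservative. All of that stands. The omitted factors may also be partly represented: staging method is tied to PSA by the exclusion in 5.4, and ARTA/docetaxel use and ADT duration may reflect perceived risk. The documents do not show how closely, so the gains above may be somewhat too high.

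It can also be said that the SAP will settle the model. For centre this is largely right: strata or a frailty are also adjustment for centre and already fit the sentence in 12.4. For the covariates it is weaker, because the set is stated there and a SAP that adds to it departs from the protocol.

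A reader might infer that the protocol commits to some 45 centre coefficients, that its confidence intervals are therefore too narrow, or that the trial is underpowered. The documents support none of these. They do not say that centre enters as indicators, they do not give 45 centres, and the event target reproduces. Even with fixed terms, eventless centres drop out in the limit and the treatment hazard ratio is still estimated.

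**Conclusion.** The point holds as a minor improvement. The stated covariate set omits the three baseline variables that define the population, and adding them gains about 0.6 to 0.9 points of power under moderate prognostic effects and about 2 to 3 points under strong ones, plus protection against chance imbalance. The way centre enters is unstated. Fixed indicator terms would mean fewer than about 3 events per parameter, a standard error about 2 to 5% too small and type I error about 5.3 to 5.6%; stratification keeps the level near 5%. The directions are well supported. The sizes rest on assumed centre numbers, centre variation, and prevalence and strength of the prognostic factors. The sample size of 1128 and the 126 events are not affected.

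**What to change.** In 12.4, or in the SAP with 12.4 amended to agree, state:

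- a Cox model stratified by centre, with centres below a set size pooled by a stated rule (for example within country), or with a shared centre frailty;
- covariates for the other four minimisation factors plus Gleason grade group, T stage and log pre-ADT PSA;
- a coding of PSA that allows for 5-alpha reductase inhibitor use, since 5.3 and 5.4 halve their PSA thresholds for these men (for example, double the value, or add an indicator);
- the model with minimisation factors only as a sensitivity analysis.

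Make the two changes together: adding covariates on top of fixed centre terms moved type I error from 5.33% to 5.57%. The cost is one sentence and no new data. Stratifying by centre costs about 0.5 to 0.7 points of power under the moderate assumptions, although none was visible in the 40-centre scenario with the strong risk factor (74.8% either way). The hazard ratio becomes conditional on the added covariates and may lie slightly further from 1 (0.604 to 0.599 in the risk HR 3 scenario), so the report should say which estimate it gives.
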